## 4.8.4 Data Collection and Participant Follow-up

After obtaining informed consent, study personnel will record the baseline data on the study CRFs. They will obtain this information directly from the participant or proxy, from the participant's medical chart, and the participant's treating orthopaedic surgeon and other health care providers. Data collection points include patient characteristics and injury details such as age, gender, comorbidities, mechanism of injury, socioeconomic status, and other injuries. Study personnel will also record the characteristics of up to three open fracture regions including the location, fracture severity, size of the wound, and degree of soft tissue injury using the Gustilo classification. 8,17,24

Surgical data and in-hospital data will be collected throughout the participant's hospital stay. Detailed information will be collected regarding the surgical management of the open fracture(s), including the time to irrigation and debridement. For each open fracture region, study personnel will record the use of staged debridements, the presence or lack of skin closure between debridements, and the use of local antibiotics at the wound. The method(s) of initial and final fracture management will also be captured. Lastly, study personnel will record the use of negative pressure wound therapy for open wounds or in the presence of open wounds surgically closed. These treatment decisions are hypothesized to be associated markers of injury severity and potential confounders of the study interventions.

Study participants will be followed at 6 weeks, 3 months, 6 months, 9 months, and 12 months from their fracture. SSIs and unplanned fracture-related reoperations will be identified at the time of diagnosis/occurrence and/or during each participant's clinical assessment and medical record review that will occur during their routine outpatient clinic visits (**Table 2**). Detailed information on the SSI including the date of diagnosis, patient signs and symptoms, culture test results, method of treatment(s), and date of resolution will be collected. Study personnel will also record details about the participants' reoperations on the CRFs (e.g., date of reoperation, type of procedure, reason for procedure, etc.). In cases where the participant does not return to the clinic, study personnel will contact the participant by telephone, text, email, standard mail, and/or will review their medical record for any SSIs, and unplanned fracture-related reoperations. If the patient reports being treated at another hospital, study personnel will obtain the medical records from the other hospital. We have used this approach in our other multi-center trials (e.g., SPRINT, TRUST, FLOW, FAITH, HEALTH, etc.). 7.23,25-27

To ensure research participant safety, serious adverse events (SAEs) will be documented at each follow-up visit and promptly submitted to the Methods Center and the local or central Institutional Review Board (IRB) or Research Ethics Board (REB) as per the required reporting processes.

Several strategies may be used to maximize follow-up including: 1) at the time of enrollment, each participant will provide their own telephone number, as well as the name and address of a primary care physician, and the names and phone numbers of three people at different addresses with whom the participant does not live with and who are likely to be aware of the participant's whereabouts; 2) participants will receive a reminder card upon discharge for their next follow up visit by the clinical site study personnel; 3) participants will receive text message reminders; 4) follow-up will coincide with normal surgical fracture clinic visits; and 5) if a participant refuses or is unable to return for the follow-up assessment, study personnel will determine his/her status with regard to

major study outcomes by telephone, text, or email contact with the participant or the provided alternate contacts. Given these are standard of care visits and the participants will be receiving ongoing orthopaedic care for their acute fractures, minimal loss to follow-up is expected. Using these techniques, we expect greater than 95% follow-up at 3 months and 90% follow-up at 12 months post-fracture.

Participants will not be deemed lost to follow-up until the 12-month visit is overdue and all attempts to contact the participant have been exhausted. Participants will not be withdrawn from the study if the study protocol was not adhered to (e.g., allocated treatment not received, missed follow-up visits, etc.). The reasons for participants being withdrawn from the study will be documented (e.g., withdrawal of consent or lost to follow up).

#### 5.0 STATISTICAL PLAN

## 5.1 Sample Size Determination

The overall objective of the trial is to determine the most effective aqueous pre-operative antiseptic skin solution for use during open fracture management. This will be achieved by comparing the effectiveness of 10% povidone-iodine versus 4% CHG surgical skin preparations. The primary outcome is the occurrence of SSI, as per the adapted CDC criteria (**Table 3**). The secondary outcome is the occurrence of unplanned fracture-related reoperations within 12 months of injury. The sample size was calculated for the primary comparison between proportions of patients with SSI in each treatment group; however, it is expected that this estimate will also provide adequate power for the secondary outcome (unplanned fracture-related reoperation) because the baseline incidence (13%) and effect size for the reoperation outcome are expected to be similar to the SSI estimates.

Assuming an ITT principle for the analysis, the sample size was calculated based on a cluster crossover design with the cluster as the unit of randomization and the patient as the unit of analysis. For complex study designs, such as a cluster-randomized crossover trial, simple formulas to calculate sample size or power may not capture the expected variability from the observed data. Simulation methods were used to obtain empirical power calculations based on a feasible number of recruiting clusters and the expected number of open fracture patients. The simulation estimates are designed to detect a difference between the treatment groups, accounting for between hospital variability inherent to a cluster-crossover trial design. We have assumed that the povidone-iodine solution will achieve a 0.65 risk ratio for SSI with a 12.5% SSI baseline incidence. This represents approximately a 4% absolute risk reduction in SSI and reoperation. This effect was deemed more conservative than data reported by Swenson et al. and was consistent with feasible recruitment goals.

Recent simulation data suggest that increasing the number of period crossovers can increase the statistical power of a given sample size. To ensure the most conservative sample size estimate, we have based our sample size assumptions using a single crossover, 2 period design. The initial power estimate assumed 10 recruiting clusters, a 10% loss to follow-up rate, and applying the between-cluster variance of 0.095 observed in the FLOW trial. Based on enrollment of a minimum of 1,540 open fracture patients, greater than 80% power would be achieved. Subsequent to the initial power calculations, the early trial experience demonstrated a need to increase the number

of clusters to obtain a feasible recruitment pace. As a result, a minimum of 12 clusters will enroll participants into Aqueous-PREP. The increase in clusters results in a marginal increase in power ( $\sim 2\%$ ).

**Table 5** below outlines the summary of the initial sample size assumptions that yield  $\geq 80\%$  power to detect difference between the treatments. These sample size estimates are rounded up to the nearest multiple of 20 to ensure balance among the clinical sites and two interventions.

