**Table 5: Sample Size Assumptions** 

Baseline SSI Risk	10% Povidone- Iodine Risk Ratio	10% Povidone- Iodine Odds Ratio	Sample Size	Sample Size Increased by 10%
10.0%	0.62	0.59	1600	1760
10.0%	0.65	0.63	1960	2100
10.0%	0.67	0.65	2200	2420
10.0%	0.70	0.68	2600	2860
12.5%	0.62	0.59	1300	1440
12.5%	0.65	0.62	1400	1540
12.5%	0.67	0.64	1600	1760
12.5%	0.70	0.67	1800	1980
14.0%	0.62	0.58	1200	1320
14.0%	0.65	0.61	1300	1440
14.0%	0.67	0.64	1500	1660
14.0%	0.70	0.67	1800	1980

**Note:** \*Between cluster ICC = 0.028; Between cluster variance\* = 0.095; Between period variance = 0; Number of clusters = 10; Number of periods = 2; Alpha = 0.05

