## 5.2.2 Analysis of the Study Outcomes

Adopting an ITT principle, multilevel regression models will be used. Correlation structures will be fit based on the observed between cluster and between period effects. A robust sandwich estimator will be used to analyze the primary and secondary outcomes.

For the primary outcome, SSI will be the dependent variable and the antiseptic solution (treatment group) will be the independent variable. For the secondary outcome, unplanned fracture-related reoperation will be the dependent variable and the antiseptic solution (treatment group) will be the independent variable. For both analyses, multiple imputation will be used to handle missing data.

As the optimal methods for analyzing cluster crossover trials continue to evolve, the final statistical modeling technique to be used will be determined in accordance with contemporary best practices prior to the completion of participant follow-up. A separate Statistical Analysis Plan will be developed prior to study closeout. **Table 6** below shows a summary of the study outcomes, corresponding hypotheses, and currently proposed methods of analysis.

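### Section 5.1 claims more than 80% power for 1,540 enrolled with 10% loss, but its own inputs give about 76–78% (about 79–80% with 5% loss)

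*Combined protocol and SAP*

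**What the plan says.** The effect assumption in section 5.1 is explicit: "We have assumed that the povidone-iodine solution will achieve a 0.65 risk ratio for SSI with a 12.5% SSI baseline incidence". The design assumptions follow: "The initial power estimate assumed 10 recruiting clusters, a 10% loss to follow-up rate", with a between-cluster variance of 0.095. The Table 5 note adds "Between period variance = 0; Number of clusters = 10; Number of periods = 2; Alpha = 0.05" and an ICC of 0.028. From these the section concludes: "Based on enrollment of a minimum of 1,540 open fracture patients, greater than 80% power would be achieved".

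In Table 5 the design row (12.5%, risk ratio 0.65) shows 1,400, raised by 10% to 1,540. The table is introduced as listing sizes that yield at least 80% power.

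On method, the section says "Simulation methods were used to obtain empirical power calculations based on a feasible number of recruiting clusters". It names neither the test applied to each simulated data set nor the number of runs. It also says of the later move from 10 to 12 clusters: "The increase in clusters results in a marginal increase in power", put at about 2%. Section 5.2.2 plans the analysis: "A robust sandwich estimator will be used to analyze the primary and secondary outcomes". Section 4.8.4 gives the expected retention: "we expect greater than 95% follow-up at 3 months and 90% follow-up at 12 months post-fracture".

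**The concern.** The plan gives enough inputs to recompute the power, and the result falls below the stated figure. With one crossover and zero period variance, each cluster acts as its own control. Power should therefore lie close to that of a simple two-proportion comparison, and that comparison needs about 1,515 evaluable patients for 80%, not 1,400.

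This is the power statement for the primary outcome. At the declared minimum enrolment and declared loss, the type II error is about 22–24% rather than below 20%, so a null result would be read against too favourable a figure. Section 5.1 also relies on the same size for the reoperation outcome, where section 4.8.4 itself expects 90% follow-up.

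**Working it through.** **Inputs.** p1 = 0.125 and p2 = 0.65 × 0.125 = 0.08125 (section 5.1). Alpha 0.05, 10 clusters, 2 periods, period variance 0 (Table 5 note). Cluster variance 0.095 (section 5.1). Equal allocation: 77 per treatment per practice in section 3.1, and 10 × 2 × 77 = 1,540. Section 5.1 does not state sidedness; I take two-sided from the confidence intervals in section 5.2.1. The variance is on the logit scale, since 0.095 / (0.095 + π²/3) = 0.028, which is the stated ICC.

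**Evaluable numbers.** 1,400 × 1.10 = 1,540 reproduces Table 5. Then 1,540 × 0.90 = 1,386 and 1,540 × 0.95 = 1,463.

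**Formula.** With n = N/2 per arm and p̄ = 0.103125,

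power = Φ{ [ (p1 − p2)√n − 1.96√(2p̄(1 − p̄)) ] / √(p1(1 − p1) + p2(1 − p2)) }.

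At N = 1,386: (0.04375 × √693 − 1.96 × 0.4301) / 0.4290 = (1.1517 − 0.8430) / 0.4290 = 0.720, so power is 76.4%. Solving for 80% gives N = 1,515.

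**Crediting the crossover.** With period variance 0, the within-period and between-period correlations are equal. The design effect is then 1 + (m − 1)ρ − mρ = 1 − ρ = 0.972. Dividing N by 0.972 is a generous credit, because 0.028 is the latent-scale ICC. N for 80% becomes 1,472.

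**Simulation.** Random-intercept logistic model, variance 0.095, 10 clusters, 2 periods, 100,000 runs or more per case, with the 12.5% read both as a conditional and as a marginal risk. The stratified (Cochran-Mantel-Haenszel) test had type I error of about 5%.

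| Evaluable N | Formula | Formula, N/0.972 | Simulated stratified test |
|---|---|---|---|
| 1,386 (10% loss) | 76.4% | 77.6% | 76.8–77.5% |
| 1,400 (Table 5) | 76.8% | 78.0% | 77.3–77.9% |
| 1,463 (5% loss) | 78.6% | 79.7% | 79.0–79.7% |
| 1,540 (no loss) | 80.6% | 81.7% | 81.2–81.7% |

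**Other tests at 1,386.** Fixed-cluster logistic Wald gives 77.4%. A random-intercept likelihood ratio test gives 77.9% (1,500 runs, simulation error about 1 point). Log odds ratio, log risk ratio and arcsine formulas give 75.5–76.8%. A sandwich with small-sample correction and t reference gives about 67%, as does a cluster-level paired t. The uncorrected sandwich z gives about 79.5–80.0% at 1,386 and 1,400, but its type I error is 9.5–9.8%.

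**Rest of Table 5.** Crediting 0.972, nine of the 12 rows give 79.5–83.9% at their stated N, so the method recovers most of the plan's own figures. The exceptions are three 12.5% rows:

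| Risk ratio (12.5% baseline) | Stated N | Power, without / with 0.972 | N for 80%, without / with 0.972 |
|---|---|---|---|
| 0.65 | 1,400 | 76.8 / 78.0% | 1,515 / 1,472 |
| 0.67 | 1,600 | 77.0 / 78.2% | 1,722 / 1,674 |
| 0.70 | 1,800 | 73.3 / 74.5% | 2,118 / 2,058 |

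With the credit, the shortfalls in N are about 5%, 5% and 14%. Two irregularities need no model. The 12.5%/0.70 and 14%/0.70 rows share N = 1,800, although the lower baseline must need more patients. And 1,960 × 1.1 = 2,156, which rounds up to 2,160 rather than the printed 2,100; 1,900 × 1.1 = 2,090 would round up to 2,100.

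**Loss inflation.** Offsetting 10% loss requires 1,400 / 0.9 = 1,556, not 1,540. This costs only about 0.4 points (76.8% versus 76.4%). The main cause is the base of 1,400.

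**Ten to 12 clusters, N = 1,400.** Stratified z: 77.7% to 77.6%. Uncorrected sandwich z: 79.8% to 79.3%. Corrected sandwich t: 67.7% to 69.4%. Paired t: 66.6–67.3% to 68.6–69.3%. A gain near 2 points appears only with tests that start near 67%. No test tried gives both that gain and 80% at 1,400.

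**The case against.** The strongest reply is that power depends on the test, the section names none, and the only estimator the plan names is a robust sandwich. Used without correction, that gives almost exactly 80% at 1,400. This may well be where the figure came from. It does not rescue the claim, because a test with nearly 10% type I error is not a test at the stated alpha of 0.05, and even then 1,386 gives about 79.5–80.0% rather than clearly more than 80%. What stands is that 76–78% belongs to stratified and model-based tests; small-sample-corrected ones give about 67%.

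Second, sidedness is inferred. A one-sided test would give 85.0% at 1,386, but nothing in the plan indicates one.

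Third, the primary outcome closes 30 or 90 days after definitive surgery, so 5% loss is arguably the relevant case, and the gap is then only 0.3–1.4 points. That is fair, but 10% is the loss the power statement itself assumes.

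Fourth, if 12 practices each reach 154 patients, enrolment is 1,848. After 10% loss 1,663 remain, and power is 83.5–84.6%. This is a real mitigation in practice. However, section 4.6.2 treats 77 per treatment as an ideal, and the claim is attached to 1,540.

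Fifth, simulation error could contribute. If true power is 77.8%, a simulation returns 80% or more in about 13% of cases with 500 runs and 5% with 1,000. With the number of runs unstated this cannot be excluded, but it would explain the error without making the figure right.

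**Conclusion.** The concern holds. For two-sided tests that keep alpha at 0.05, power at 1,540 enrolled is about 76–78% at the stated 10% loss, a shortfall of about 2–4 points, and about 79–80% at 5% loss. It exceeds 80% (about 81%) only with essentially complete data, and only for stratified or model-based tests; corrected sandwich or cluster-level tests with 10 clusters fall well below. The result rests on two-sided testing, equal allocation and the plan's own variance inputs. The gap is modest and 1,540 is a minimum, so this corrects a stated figure and some table entries and is no objection to the design.

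**What to change.** 1. Restate the power for 1,540 enrolled as about 77% with 10% loss, or about 79% with 5% loss, and say that this is for a stratified or model-based two-sided test.
2. Name the test behind the simulation, its simulated type I error with 10 and 12 clusters, and the number of runs. Use the same test for the power figure and for the claimed gain of about 2%. If the planned analysis is a sandwich estimator with small-sample correction, report the power for that, which was about 67–69% at 1,400.
3. Recompute the 12.5% rows at risk ratios 0.65, 0.67 and 0.70: about 1,515, 1,720 and 2,120 evaluable, or about 1,475, 1,675 and 2,060 if the 0.972 design effect is credited. Reconcile the 1,960 and 2,100 cells.
4. Inflate for loss by dividing by 0.9.

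The cost is rewording, a table correction, a sentence on the simulation and a slightly less favourable figure. No added recruitment is needed. If a true 80% at 10% loss is wanted instead, enrolment would need to be about 1,640–1,690 (1,472 / 0.9 = 1,636; 1,515 / 0.9 = 1,684).

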**Table 5: Sample Size Assumptions** 

Baseline SSI Risk	10% Povidone- Iodine Risk Ratio	10% Povidone- Iodine Odds Ratio	Sample Size	Sample Size Increased by 10%
10.0%	0.62	0.59	1600	1760
10.0%	0.65	0.63	1960	2100
10.0%	0.67	0.65	2200	2420
10.0%	0.70	0.68	2600	2860
12.5%	0.62	0.59	1300	1440
12.5%	0.65	0.62	1400	1540
12.5%	0.67	0.64	1600	1760
12.5%	0.70	0.67	1800	1980
14.0%	0.62	0.58	1200	1320
14.0%	0.65	0.61	1300	1440
14.0%	0.67	0.64	1500	1660
14.0%	0.70	0.67	1800	1980

**Note:** \*Between cluster ICC = 0.028; Between cluster variance\* = 0.095; Between period variance = 0; Number of clusters = 10; Number of periods = 2; Alpha = 0.05

#### 5.2 Statistical Methods

## 5.2.1 Analysis Plan Overview

A detailed statistical analysis plan will be published prior to the completion of the trial. The analysis and reporting of the results will follow the CONSORT guidelines for reporting of both pragmatic trials and cluster-randomization trials. The process of patient enrollment and flow throughout the study will be summarized using a flow-diagram. Patient demographics and baseline outcome variables will be summarized using descriptive summary measures expressed as mean (standard deviation) or median (interquartile range) for continuous variables depending on the distribution, and number (percent) for categorical variables. An ITT principle will be adopted to analyze all outcomes and the unit of analysis will be the individual patients. Missing data will be assumed to be missing at random and will be handled with multiple imputation.

The primary analysis will compare the treatment groups on the SSI outcome and the secondary analysis will compare the unplanned fracture-related reoperation outcome. The secondary comparison will be conducted in accordance with best practice guidelines for secondary analyses. For all models, the results will be expressed as relative measure of effect (odds, risk, or hazard ratios) and corresponding two-sided 95% confidence intervals.

## 5.2.2 Analysis of the Study Outcomes

Adopting an ITT principle, multilevel regression models will be used. Correlation structures will be fit based on the observed between cluster and between period effects. A robust sandwich estimator will be used to analyze the primary and secondary outcomes.

For the primary outcome, SSI will be the dependent variable and the antiseptic solution (treatment group) will be the independent variable. For the secondary outcome, unplanned fracture-related reoperation will be the dependent variable and the antiseptic solution (treatment group) will be the independent variable. For both analyses, multiple imputation will be used to handle missing data.

As the optimal methods for analyzing cluster crossover trials continue to evolve, the final statistical modeling technique to be used will be determined in accordance with contemporary best practices prior to the completion of participant follow-up. A separate Statistical Analysis Plan will be developed prior to study closeout. **Table 6** below shows a summary of the study outcomes, corresponding hypotheses, and currently proposed methods of analysis.

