## STUDY SUMMARY

Methodology	Cluster randomized crossover design.
Coordinating Center	This study will be centrally coordinated by the Methods Center at the Center for Evidence-Based Orthopaedics (CEO), McMaster University, Hamilton, Ontario and by the Administrative Center within the Department of Orthopaedics at the University of Maryland, R Adams Cowley Shock Trauma Center, Baltimore, Maryland.
Clinical Sites	At least 12 clinical sites. Additional clinical sites will be included or removed as needed.
Background	The prevention of infection is the single most important goal influencing peri-operative care of patients with open fractures. Standard practice in the management of open fractures includes sterile technique and pre-operative skin preparation with an antiseptic solution. The available solutions kill bacteria and decrease the quantity of native skin flora, thereby decreasing surgical site infection (SSI).  While there is extensive guidance on specific procedures for prophylactic antibiotic use and standards for sterile technique, the evidence regarding the choice of antiseptic skin preparation solution is very limited for open fracture surgery.
Objectives	The overall objective is to compare the effectiveness of aqueous pre- operative antiseptic skin preparation with 10% povidone-iodine versus 4% chlorhexidine gluconate (CHG) for the management of open fractures. A ranked order for assessing effectiveness will be used with surgical site infection (SSI) as the primary comparison and unplanned fracture-related reoperations as the secondary comparison.
Subgroup Objectives	We will explore if the pre-operative antiseptic skin solutions have different magnitudes of effect on SSI within three clinically important open fracture subgroups: severity of open fracture, location of fracture, and severity of wound contamination.
Diagnosis and Main Inclusion Criteria	All patients 18 years of age or older who present to a recruiting hospital for treatment of an open fracture(s) of the appendicular skeleton will be screened for participation within 3 weeks of their fracture. Eligible patients must receive surgical debridement of their open fracture wound(s) within 72 hours of their injury and the open fracture(s) must be managed definitively with a surgical implant (e.g., internal fixation, external fixation, joint prosthesis, etc.).

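### Section 5.2.2 proposes a sandwich variance with as few as 12 clusters and no few-cluster correction; in its ordinary form the nominal 5% primary test runs at about 9%

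*Combined protocol and SAP*

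**What the plan says.** Section 5.2.2 plans multilevel regression for SSI and for unplanned reoperation, with correlation structures chosen from the observed cluster and period effects, and adds: "A robust sandwich estimator will be used to analyze the primary and secondary outcomes". It presents these as "currently proposed methods of analysis" and says that "the final statistical modeling technique to be used will be determined in accordance with contemporary best practices prior to the completion of participant follow-up", with a separate SAP to follow. Section 5.2.1 promises two-sided 95% intervals, and both sections call for multiple imputation.

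The randomised unit is the orthopaedic practice (section 3.1). Section 5.1 says "a minimum of 12 clusters will enroll participants into Aqueous-PREP", and the Study Summary treats this as a floor: "At least 12 clinical sites. Additional clinical sites will be included or removed as needed". The sample-size table used fewer: "Number of clusters = 10; Number of periods = 2; Alpha = 0.05". On power, section 5.1 says "Based on enrollment of a minimum of 1,540 open fracture patients, greater than 80% power would be achieved".

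No section gives a clustering level, a small-sample correction, or degrees of freedom. Sensitivity analysis 1 in section 5.2.4 varies the model and its correlation structure only.

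**The concern.** A sandwich variance is estimated from the spread of cluster-level contributions. With about a dozen clusters it is biased downwards and is itself noisy, so comparing the statistic with a normal distribution rejects too often. An uncorrected, practice-clustered sandwich with a normal reference would satisfy section 5.2.2 as written.

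The primary test and its interval are at stake. At a 9% error rate, a nominal 95% interval covers about 91%, and the chance of wrongly declaring one solution better is nearly twice the stated alpha. The power claim in section 5.1 also depends on which version is used.

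**Working it through.** **Inputs.** SSI risk 12.5%, risk ratio 0.65, cluster variance 0.095, period variance 0, 2 periods and 10 clusters (section 5.1, Table 5); 12 clusters (section 5.1). Follow-up: "we expect greater than 95% follow-up at 3 months and 90% follow-up at 12 months post-fracture". Hence 0.95 × 1,540 = 1,463 analysed for SSI, taken as 1,464 (24 practice-period cells of 61). Equal cluster sizes are an assumption.

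**Consistency of the inputs.** 0.095 / (0.095 + π²/3) = 0.028, the ICC in the Table 5 note. (0.08125/0.91875) / (0.125/0.875) = 0.62, the tabulated odds ratio.

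**Method.** Simulate events in practice k with logit risk a(treatment) + u(k), where u(k) ~ N(0, 0.095). Estimate b = logit(p1) − logit(p0). The contribution of practice k is

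e(k) = [Y(k1) − n(k1)p1] / [N1 p1(1−p1)] − [Y(k0) − n(k0)p0] / [N0 p0(1−p0)].

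- Clustered on practice: V = Σ e(k)².
- Clustered on practice-period: square each cell's part separately, then sum.
- Corrected: V × K/(K−1). With equal clusters and treatment as the only covariate, this equals the Kauermann-Carroll correction (12/11 = 1.0909 at K = 12).
- Reject when |b|/√V exceeds 1.96, or the t quantile with K−1 df.

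**The plan's own figure.** With 10 clusters, 2 periods and N = 1,400, the plain two-proportion formula gives 76.8% power. Simulation with the uncorrected practice sandwich and normal reference gives 79.5% (12.5% read as the marginal risk) to 80.0% (read as the risk at the average practice). The stated 80% is therefore reproduced to within a point.

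**Type I error, 12 clusters, 2 periods, N = 1,464** (40,000 runs, Monte Carlo SE about 0.14 points):

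| Version | Type I error |
|---|---|
| Practice, uncorrected, normal | 8.8% |
| Practice, K/(K−1), normal | 7.7% |
| Practice, uncorrected, t(11) | 5.9% |
| Practice, K/(K−1), t(11) | 5.1% |
| Practice-period, normal | 2.9% |

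The same sandwich on a fitted random-intercept logistic model gives 8.6%, 5.9% with t(11), and 5.0% with both adjustments. For reoperation (13%, 0.90 × 1,540 = 1,386 analysed) the figures are 8.7% uncorrected and 5.1% corrected.

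**Number of periods.** About 24 months of roughly two-month phases (section 4.6.4) is about 12 periods. With 12 clusters, N = 1,400 and 12 periods, the uncorrected practice version runs at 8.8%, the corrected one at 5.1%, and the practice-period version at 4.3%. Practice-period clustering is conservative because it ignores that a practice's effect cancels between its two treatments. That loss shrinks as the cells get smaller.

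**Number of clusters** (N = 1,400, 2 periods):

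| K | 10 | 12 | 14 | 20 | 30 |
|---|---|---|---|---|---|
| Uncorrected, normal | 9.7% | 9.0% | 8.3% | 7.1% | 6.2% |
| K/(K−1), t(K−1) | 5.2% | 5.1% | 5.2% | 4.9% | 4.7% |

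**Unequal sites** (coefficient of variation 0.5 / 0.8, assumed, not in the documents): 9.6% / 10.9% uncorrected; 5.6% / 6.3% with Kauermann-Carroll and t(11).

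**Power at risk ratio 0.65, 2 periods:**

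| Setting | Uncorrected, normal | K/(K−1), t(K−1) |
|---|---|---|
| 10 clusters, N = 1,400 | 79.4% | 67.4% |
| 12 clusters, N = 1,400 | 79.0% | 68.9% |
| 12 clusters, N = 1,464 | 80.7% | 71.1% |
| 12 clusters, N = 1,540 | 82.3% | 73.0% |

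**Interval width at 12 clusters:** 2.201 × √(12/11) = 2.299, and 2.299 / 1.96 = 1.17, so about 17% wider.

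Multiple imputation, common period effects and data-driven choice of correlation structure were not simulated.

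**The case against.** The strongest reply is that the plan openly defers this. The methods are provisional, a published SAP is promised, and degrees-of-freedom rules are normal SAP content. That stands as far as it goes: a reader might infer that the trial's final test will be mis-sized, and the documents do not show that. But the sandwich is the estimator named now, nothing withdraws it, and the promise to follow best practice does not commit to a few-cluster correction.

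Second, 12 is a minimum. More clusters help only slowly: the uncorrected form still runs at about 7% with 20.

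Third, a reader might take the possible error rate to run from 3% to 9%. The 3% end belongs to the 2-period layout used only for sample size. With about 12 periods it is about 4%, and practice-period clustering is the less natural reading when practices are randomised.

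Fourth, a model-based test could be used instead. That is right. A practice-only random-intercept likelihood-ratio test ran at 5.0% on Table 5 inputs. It would be too strong to say that it is valid only when the practice-period variance is zero. With an assumed variance of 0.019 (20% of 0.095, not in the documents) it ran at 6.6% in 2 periods (N = 1,464) and 5.6% in 12 periods (N = 1,440). With a t(11) reference it ran at 4.2% in 2 periods (N = 1,440).

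**Conclusion.** The concern holds as a correctable fault in the proposed method. With 12 equal clusters and Table 5 inputs, the ordinary form of the named estimator runs at about 9% for both outcomes, whatever the number of periods. A standard correction with a t reference restores about 5%. With unequal site sizes, which recruitment sampling, late-joining sites and site withdrawal make likely (sections 4.3.2, 4.6.4, 4.6.5), the corrected form drifts to about 5.6% to 6.3% under the assumed variation, so it is much better but not exact.

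The power statement is not tied to a test. The uncorrected sandwich gives about 80% at Table 5's 10 clusters and 1,400 patients, and the corrected one about 67%. A reader might infer that the sponsor's simulation used the liberal test. The documents do not support that: section 5.1 does not name the test, and over the twelve rows of Table 5 the uncorrected version gives anything from 76.7% to 84.6%, so one matching row is weak evidence.

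**What to change.** Before unblinding, state in section 5.2.2 and the SAP one of the following:

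1. The sandwich is clustered on orthopaedic practice, with a named small-sample correction (for example Kauermann-Carroll) and a t reference with number of clusters minus one degrees of freedom. State how those degrees of freedom enter the multiple-imputation pooling.
2. The sandwich is replaced by a model-based test that names its random effects (practice only, or practice and practice-period) and its degrees-of-freedom rule.

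Then restate the power in section 5.1 for the chosen test, giving the number of clusters and periods and the number analysed.

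The cost is a few lines of text and standard software options. The downside is that stated power falls, to about 71% for option 1 with 12 clusters and 1,464 analysed, and intervals are about 17% wider than the uncorrected ones. More clusters recover part of this: with 20 clusters and 1,464 analysed, option 1 has about 75%.
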